3.6 Sample size calculations

Number of HCPs for observation

The methodology knowledge base for stepped wedge trial designs is still relatively limited (Taljaard et al 2017). Quantities which need to be specified when designing them include: the number of clusters (HCFs) to participate; the number of steps; the number of steps per HCF in which assessments are made. For the current trial the number of HCPs to be observed and the number of assessments made per HCP per step are also needed. The most critical of these is the number of clusters to participate. Although the literature regarding sample size is in its infancy there is clear consensus that with few clusters the design lacks robustness (Barker et al, 2016 and Martin et al 2016). There are up to 20 HCFs available in which to conduct the trial. The incompleteness of the proposed trial design may compromise the integrity of the trial if fewer clusters are used. Thus, all available HCFs are planned to be included but calculation will be done on a minimum of 18 HCF for a conservative approach.

The number of steps possible is limited to six because it is not feasible to conduct more than six training sessions with the budget available. The duration of each step is set at six or seven weeks rather than one month to allow enough time for data collectors to accommodate with the observed HCP's roster and schedules within the appropriate steps.

In principle, the target number of HCPs for observation for each primary outcome should be three per HCF, however recognising this may not be feasible (especially in smaller facilities with limited staff present), the minimum number of HCPs to participate has been set at two per HCF, accepting that both HCPs would be required to take part in the trial and accept being observed completing both ANC and PNC visits in all four assessment periods planned for their HCF; this number is both feasible for this trial and expected to ensure adequate robustness to examine the hypotheses of interest (Girling and Hemming 2016).

Observation of each HCP in multiple assessment periods will improve the power of the trial to detect an improvement in outcomes, since underlying differences between individual HCPs will be able to be modelled using random HCP effects. However, shift patterns will limit the availability of participating HCPs, so at some HCFs it may be necessary to conduct observations on two different dates within a step to be able to observe at least two HCPs in each assessment period. In facilities where both ANC and PNC clients are seen by each participating HCP observations for both primary outcomes will be able to be completed using the same HCPs. For other facilities, where ANC and PNC clinics are completed by different sets of staff on any given shift it may be preferable to recruit 4 to 6 HCPs, some to be observed providing ANC and others PNC. This would enable HCPs in both clinics to be observed on some observation days, thereby reducing the number of observation days in the assessment period. **Box 2** summarises the sample size planned.

Each interaction (ANC and PNC) observed will be assessed for the corresponding primary outcome.

The R shiny app ($\frac{\text{Hemming}}{\text{Memming}}$, 2019) was used in February 2020 to perform power calculations for this design, using a continuous response, with a standard deviation of σ . The standard deviation, σ , is the square root of the total variance, which aggregates the various components of variance. The app is not designed for the additional level of observation within HCP, so the data considered for purposes of sample size calculation is the mean across four observations for each HCP at the HCF.

Box 2: Sample size details

Number of clusters (HCFs):	18
Number of steps:	6 (8 assessment periods)
Duration of steps:	6-7 weeks
For each HCF:	
Number of HCPs per primary outcome*:	3 (or 2)
Number of periods in which care at HCF is assessed:	4
	(periods 1, 3, 5 and 7
	or 2, 4, 6 and 8)
Number of HCPs assessed for each primary outcome per assessment period:	At least 2
Number of HCP-client interactions assessed for each primary outcome per HCP assessed in an assessment period	4

^{*} where clinics combine ANC and PNC clients the same HCPs can be used for both; where ANC and PNC clinics are separate different sets of HCPs may be used.

Table 4 indicates the standardised differences detectable with this design if 3 HCPs are observed in each assessment period at each HCF. Additionally, Table 5 indicates differences detectable if only 1 HCP is recruited and observed for each HCF.

Several different sets of values for the various ICCs have been considered, based on those estimated from the analysis of data for compliance with standards in Malawi. The stepped wedge trial in Malawi using Standards-based audits estimated the within period ICC (the correlation between responses for pairs of individuals within the same cluster and step) to be 0.16 and the CAC (cluster autocorrelation: correlation between pairs of population means from the same cluster in different steps) to be 0.38. As that trial was cross-sectional the intracluster autocorrelation (IAC: correlation between responses from an individual in different steps) was not estimable.

Table 4: Standardised differences detectable with 80% power using a continuous response in a closed cohort design

Within period	CAC	3 HCPs	observed in assessment		bserved in assessment
ICC		occasion	ussessiment	occasion	assessinent
		IAC=0.6	IAC=0.8	IAC=0.6	IAC=0.8
0.2	0.02	0.64	0.60	0.86	0.73
	0.4	0.62	0.57	0.83	0.70
0.4	0.4	0.75	0.72	0.90	0.82
0.5	0.1	0.81	0.81	0.95	0.90
	0.9	0.50	0.44	0.67	0.55

Based on the range of combinations which were estimated for that trial it is expected that with this design an improvement of 0.81σ , would be detectable with at least 80% power if all three HCPs at each HCF are assessed on each assessment occasion. If only one HCP per HCF participates the improvement detectable with 80% power would be 0.95σ . The magnitude of σ depends on at least three sources of variation which are aggregated into the total variance (σ^2): residual variation (σ^2_{error}), and the variances for each of the random effects for: HCF (σ^2_{HCF}), HCP within HCF ($\sigma^2_{HCP|HCF}$), and possibly HCF by month ($\sigma^2_{HCF*month}$).

The residual variation (σ_{error}) is assumed not to exceed 0.2 for individual assessments, so the residual variation for means for assessment of 4 visits would not exceed 0.1. For the random effects we assume that each of σ_{HCF} , $\sigma_{HCP|HCF}$ and σ_{HCF^*month} does not exceed 0.15 in value. (A standard deviation for HCPs ($\sigma_{HCP|HCF}$) of 0.15 would occur if the means for HCPs in a given month have a range of about 0.6 and 65% of the means are within a range of 0.3, within a possible range of values of 1.0 (Figure 2 displays two such distributions). With these values the overall standard deviation would then not exceed 0.28 =sqrt(0.01+0.0225*3), when means of 4 observations for 3 HCPs per HCF are used and an improvement of 0.81*0.28=0.23 would be detectable with at least 80% power. For other scenarios the upper limits on the difference detectable is indicated in the table below. If all HCPs are assessed as assumed the absolute differences detectable with 80% power are likely to be smaller than indicated in the table, since the variances are unlikely to take values as large as assumed.

[figure not shown]

Figure 2: Examples of distributions with standard deviation of 0.15

However, it is expected that some HCFs will only have two HCPs able to participate in the trial, and that in some steps when assessment is planned some HCPs will not be assessed due to logistic reasons. These reductions in the volume and structure of data would increase the difference detectable. Sample size formulae are not available to adjust the sample size if some HCPs are not assessed on all planned occasions. To examine the likely impact of such shortfalls in the planned sample size two small simulations were performed to examine the impact on standard errors of the estimated intervention effect and thus of the difference detectable:

- i) A reduction in the number of HCPs available at half of the HCFs from 3 to 2;
- ii) Observation of only one (of 3) HCPs per HCF in each assessment period.

For each scenario a dataset was generated using the design details and an intervention effect of 0.1 (approximately 1 additional item addressed on average). Each dataset was analysed as planned. For each dataset ten subsets were then also derived and analysed as planned.

The impact of a reduction in the number of HCPs participating per HFC was consistent with the reduction in sample size with the average increase in the standard error of the estimate being 10%. The difference detectable would similarly be expected to increase by 10% if only 2 HCPs participate in nine of the HCFs.

The impact of only observing one of three HCPs on each assessment occasion was amplified beyond that expected based on sample size alone. On average the standard error more than doubled, whereas based on sample size changes an increase of 73% would be expected. This amplification is due to the reduction in the numbers of participants observed longitudinally to just one or two of the three.

These simulations indicate that there is greater value in ensuring that each HCP who participates is observed in multiple assessment periods than in increasing the number of HCPs who participates or the number of replications of observations beyond 4.

Table 5 indicates that if one HCP rather than three participate per HCF there would be some increase in the difference detectable; this would depend on the ICCs involved, but would not exceed about 35%. By contrast if different HCPs are observed in different assessment periods

the difference detectable increases more substantially. Therefore for outcomes observed only in ANC or PNC interactions there will be greater power to detect a given difference if the same HCP is observed in each assessment period, or if all participating HCPs are able to be observed completing a single assessment for each secondary outcome than if different HCPs are observed in the planned assessment periods.

Table 5: Differences detectable

Observation s / HCP	Upper limit on standard deviation	Difference detectable (>80% power)	
		3 HCPs / HCF	1 HCP / HCF
4	√(0.01+0.0675)=0.278	0.23	0.26
1	√(0.04+0.0675)=0.328	0.27	0.31

Covid-19 situation and impact on sample size

In terms of data collection, the attendance of ANC-PNC could also be reducted due to restrictions or to the fear of perceived risks associated with coming to seek care; if not enough women seek care, this would, in turn, impact the power of the study. The steps were defined as 6-7 weeks long to allow ample opportunity for interactions to be observed, there is thus some capacity for data collectors to add visits if needed to reach the necessary 3-4 observations per healthcare provider. The moderate number of necessary subjects seems to pose a low risk.

There is very low but existant risk that any gathering is prohibited. If that happens, the capacity of the program to deliver training while respecting the steps within the trial would be compromised. Trainings would have to be postponed until authorized, which would in turn affect the difference detectable. Although this is a non-negligible risk to the study, there may be leeway to reduce the length of the steps to enable the planned steps to be completed. At worst-case scenario, if any gathering is prohibited for the whole duration of the study, the intervention will ultimately not be able to be delivered to all HCFs and the trial would be aborted. Regarding capacity-building however, training would still resume as soon as possible so healthcare providers still have the benefits of it. As of 13th of May 2020, no indication from the MoH has suggested that all gatherings would be prohibited.

3.7 Data collection

Data sources

The main sources of information will include:

1. Observation of ANC-PNC visits for assessment of delivery of care. The tools will be developed ahead of the trial start. Following consultation with in-country partners, they will be converted onto a standardised platform (paper or electronic) for use for data collection.

All data collection will be undertaken by clinically trained data collectors external to the HCF with supervision from CSSI-CRASH and remote support from LSTM. To enhance acceptability of observations and minimize any potential unease for the women to be observed, the data collectors will be exclusively females. Data collectors will receive training on data retrieval and collection; with regard to observation of ANC-PNC visits, specific training on research methods covering consenting, ethical aspects of observation, data anonymization, rapport building, and observation techniques will be provided. As specified in this document, data collection will take place at specified time points. For the observation, we expect data be collected for 4 consecutive clients coming for ANC per HCP observed for ANC and the same for PNC. In each assessment period there would be a total of 8 to 12 clients per facility for each consultation type (through as many visits as needed to observe 2 to 3 HCPs per facility). The data collection tools will therefore aim to capture the service provision of the HCP observed. Anonymous ID codes within HCF will be agreed and applied in the final database for each HCP observed.

2. Healthcare facility records and register review for extracting data on equipment, consumables, medications as well as elements of infrastructure availability, staff availability (by cadres and type of services provided; though no personal details of individual staff members), and uptake of services (number of women attending for ANC and PNC services, morbidities and mortalities related to pregnancy and childbirth, specific aspects of care provisions (all as pooled data for a specified month, with no individual details extracted).

Data collection

Before commencing either intervention the HCFs selected to participate in the trial will be surveyed to ascertain the availability of human resources and the components identified as in principle needed for the delivery of the essential components defined.

Delivery of essential components will be assessed through the observation of ANC-PNC visits by external data collectors. At each healthcare facility at least two healthcare providers will be observed in each assessment period. For each assessment period one observation day will be scheduled for each HCF to be assessed in the period. All participating HCPs on duty within the HCF will be observed completing four ANC/PNC visits on each of these days. If only one participating HCP is observed an additional observation day will be scheduled within the same assessment period to observe at least one more participating HCP within the HCF. Each HCP should be observed in at least three of the four assessment periods for their HCF. The observers will plan with the healthcare facilities to observe four consultations for each HCP who is on duty in accordance to rosters.

The availability of equipment and consumables for each component of care for ANC-PNC services quarterly (every 2 steps in the trial schedule) will be assessed on the first possible day of the following quarter. This data will allow for the analysis to assess if the delivery of essential components was linked or not by the availability of equipment and consumables. Finally, the number of women attending for and receiving care will be extracted quarterly

using the official routine facility registers. The healthcare facility assessment tool for equipment, consumables and use of services has been developed in line with the specific ANC-PNC service provision elements and with usual facility assessment tools used by CMNH-LSTM in baseline assessment (See **Appendix 3**).

Covid-19 situation

As of 13th of May, borders are closed and international flight barred, public transportation interrupted and meetings of 50 people or more prohibited. Our focal point from MoH and implementation partners from CSSI-CRASH consortium have so far not advised against conducting the study, which will be set only within N'Djamena and thus not require any interregional travels that may be impeded in the future. To date no other measures that could impede the delivery of this trial have been identified.

Data collectors will observe all regulations from healthcare facilities, district, regional and national COVID-19-related guidelines. Prior to the commencement of this study a robust COVID-19 risk assessment, in line with LSTM Research Governance & Ethics guidance. In addition, COVID-19-related risks and situations will be included in the regular safeguarding assessment before data collection. Close monitoring will be done in partnership with MoH and CSSI-CRASH to ensure that the latest guidelines are followed, and trial adapted as and when required. No research activities will be carried out if they contravene the guidelines until the situation settles. LSTM Ethics Committee will be informed about the revised timeline.

Data collectors are expected to visit facilities in-country COVID-19 guidelines allow. There are still many unknowns when this virus will come to an end, Data collectors will be expected to wear surgical masks as a minimum, as well as respect physical distancing from both healthcare providers and clients alike to ensure they pose a minimal risk of transmission during the observation. Training on barrier measures, hygiene and infection prevention and control will be part of their initial inception and refreshed regularly. If there is not enough space to allow physical distancing to be up to guidelines, they will not carry the observation. However, all facilities in the sample will be visited prior to the trial in order to ensure that this is in principle possible.

There is a potential impact of Covid-19 and containment measures on the delivery of the intervention by the CMNH international and/or national team, the retention of healthcare providers, as well as data collection. The number of participants to attend ANC-PNC is 32 per training. With facilitators, this should be a maximum of around 40 people at the same time which is still under the national guidelines. However, shall the situation evolve, it should be possible to scale down the size of the training to ensure that the number of participants complies with country guidelines. Although this would raise the cost associated with the training, substantial savings should be made on the budget as a result of reduced international travels to Chad during the ongoing pandemic to cover it. The CMNH team is working in the meantime on a full review of its training package in order to discuss country-specific contents with CSSI-CRASH and the MSP, and plan for a contingency solution where

the in-country team, CSSI-CRASH staff and previously trained Master trainers would be refreshed and supported remotely to be able to adapt to the changing environment and carry out the interventions.

3.8 Statistical analysis

Period is defined as the assessment period of the trial which observation occurred, or for which measurement took place. Data will be omitted from analysis when values are missing for either the outcome or a covariate required for the analysis of that data value. Missing data will not be replaced.

For each ANC/PNC visit observed the proportion of essential components addressed will be calculated (ECall). Data analysis will be performed using Stata version 14.2 or later. To derive an estimate of the benefit of providing ANC-PNC training, linear regression within a generalised linear mixed model (GLMM) framework will be used to analyse the primary outcome data (ECall). GLMMs are appropriate in the context of stepped wedge trial designs as they allow for clustering and address confounding of intervention effects and time (Hemming et al 2015). The analysis will include a binary intervention factor which indicates if the data were collected pre- or post- ANC-PNC training and fixed effects for study month to account for any underlying secular trend. Random effects will be included for HCF (cluster), HCP within HCF and HCF by month interaction. The effects of the intervention will be reported as an adjusted (for month, HCF and HCF by month clustering) odds ratios (OR), with 95% confidence intervals.

Reporting will follow CONSORT guidelines for reporting stepped wedge trials current at the time of publication of the results (currently Hemming et al, 2018), Available data will be analysed using an intention to treat approach and also as implemented, if there are any protocol deviations, to assess the sensitivity of results to the analysis approach adopted.

The baseline delivery of essential components has been assumed to be around 50% as the precision of estimates is poorest for this value. If the level is below 50% there will be greater potential for improvement and greater power to detect an improvement of a specified magnitude. However, if the level is close to 100% it will not be possible for a statistically significant benefit of the intervention to be demonstrated. In such circumstances administrative analyses will be conducted.

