3.2 Trial type and design

3.2.1 Trial design

A multi-dimensional incomplete stepped wedge cluster randomised trial design (SW-RCT) in a cohort of HCPs will be used to assess the effects of the intervention (Training in ANC and PNC). The study duration will be 12 months with each step being 6 or 7 weeks in duration. Each HCF will receive the intervention (ANC-PNC training) and be observed following a defined schedule. The participants will be HCPs at the participating HCFs, for whom assessments are obtained in each assessment period through observing them in the provision of ANC-PNC services. The design is summarised in **Table 3**.

The benefits of the stepped wedge design in terms of feasibility and level of proof have been described previously (Hargreaves et al 2015, Hemming et al 2015, Prost et al 2015). Each HCF will provide data for both the control and the intervention state, which increases the efficiency of the trial. Estimates of intervention effects are expected to be more precise than in a parallel trial design.

Table 3: Summary of trial design

Intervention	Training in ANC and PNC
Design	Multi-dimensional incomplete SW CRT
	Cohort
Sampling units	Primary: 18 HCFs
	Secondary: 36 to 54 HCPs (2 to 3 per HCF and per step)
	Tertiary: clients (3 to 4 observations per HCP and per step)
Data measurement per HCF	Delivery of essential components during sampled ANC-PNC visits
No. and duration of steps	Six steps, eight assessment periods – each 1.5 months long (6-7 weeks)
Trial duration	12 months
Primary Outcome	Proportion of essential components delivered during ANC-PNC visits

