3.4 Outcomes

This trial will have two primary outcomes, one around essential components for ANC, and one for essential components for PNC.

Outcome 1 (ANC): Essential components included in the composite measure of integrated services specific to ANC visits are listed below.

- EC1 = Respectful maternity care indicators:
 - Introductions, greeting the woman, consent, questions
- EC2 = Screening for Pre-eclampsia:
 - Measure BP

- Test urine for proteinuria
- EC3 = Screening for, prevention and management of Anaemia:
 - Measure Haemoglobin
 - Provide ferrous sulphate with folic acid
- EC4 = Screening for, prevention and management of Malaria:
 - Checked for clinical symptoms and test for Malaria if relevant
 - Provide treatment if needed
 - Provide bed nets if not provided yet
 - Provide Intermittent Presumptive treatment
- EC5 = Screening for, prevention and management of HIV:
 - Test for HIV
 - Provide Prevention of mother to child transmission care (PMTCT)
 - Provide anti-retroviral drugs (ARV) for mother if needed
- EC6 = Screening for, prevention and management of Syphilis:
 - Test for syphilis
 - Provide antibiotics if needed
- EC7 = Screening for, prevention and management of Tuberculosis (TB):
 - Checked for clinical symptoms and test for TB
 - First line TB drugs or referral if needed
- EC8 = Prevention of Tetanus in mother:
 - Tetanus toxoid vaccination
- EC9 = Screening and counselling for mental health and domestic violence:
 - Screening tools
 - Counselling services
- EC10 = Estimation of BMI:
 - Assess maternal height
 - Assess maternal weight
- EC11 = Prevention of post- and pre-term birth:
 - Estimate gestational age
- EC12 = Assessment of foetal wellbeing during pregnancy, Screening for multiple pregnancy, abnormal lie and presentation during pregnancy:
 - Assess growth using fundal height measurement
 - Assess foetal heart rate (FHR)
 - Abdominal palpation
- EC13 = Provide advice on birth preparedness and danger signs of pregnancy:
 - Consultation

The outcome for each ANC visit will be a score which measures the proportion of the above components that was delivered during that visit (EC_ANC).

The score will measure the proportion of essential components delivered in full. All thirteen essential components listed above are applicable for ANC. Some essential components

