- EC15b = Immunization status checked and required vaccinations offered and provided if required
- EC16b = Provide advice on danger signs in the mother and baby:
 - Consultation

The outcome for each PNC visit will be a score which measures the proportion of the above components that was delivered during that visit (EC_PNC). This score will be derived in a similar manner to the score for ANC, the difference being that three essential components used for ANC will be dropped and six others added.

The observation tool is detailed in **Appendix 2**.

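### Section 3.4 names two primary outcomes, EC_ANC and EC_PNC, but section 3.8 specifies one model for a single variable, ECall, with no visit-type term and no statement that it is fitted to each outcome

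*Protocol*

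**What the plan says.** **Two outcomes.** Section 2.3.1 lists delivery at ANC visits and delivery at PNC visits as separate outcomes. Section 3.4 is explicit: "This trial will have two primary outcomes, one around essential components for ANC, and one for essential components for PNC". It gives each visit type its own score, EC_ANC and EC_PNC. The ANC score has 13 components and the PNC score 16; the latter is formed by dropping three ANC components and adding six.

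**Sampling per outcome.** Box 2 in section 3.6 sets the number of HCPs, and four interactions per HCP and period, for each primary outcome. The same section says "Each interaction (ANC and PNC) observed will be assessed for the corresponding primary outcome". Section 3.7 plans 8 to 12 clients per facility and period for each type of consultation.

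**One variable in the analysis.** Section 3.8 states "For each ANC/PNC visit observed the proportion of essential components addressed will be calculated (ECall". It then uses a linear mixed model "to analyse the primary outcome data (ECall". The fixed effects are a pre/post training indicator and study month. For the rest: "Random effects will be included for HCF (cluster), HCP within HCF and HCF by month interaction". EC_ANC and EC_PNC do not appear in section 3.8, and ECall appears nowhere else in the protocol.

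**One outcome elsewhere.** Table 3 in section 3.2.1 gives the primary outcome as "Proportion of essential components delivered during ANC-PNC visits". In section 3.6, the paragraph introducing Table 5 discusses outcomes seen in only one type of visit and then calls the outcomes concerned secondary.

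**The concern.** The outcomes section and the analysis section do not describe the same primary analysis. A statistician who follows section 3.8 as written would stack ANC and PNC visits and report one training effect. That effect would answer neither question posed in section 3.4, and a gain confined to one service could be presented as improved ANC-PNC care. A statistician who follows section 3.4 would report two effects. The protocol allows both, so the choice could be made after the results are known.

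**Working it through.** **1. Following the primary variable through the protocol**

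| Place | What is primary |
|---|---|
| 2.3.1, 3.4 | Two outcomes: EC_ANC (13 components), EC_PNC (16 components) |
| 3.6, Box 2; 3.7 | Sampling planned for each outcome or consultation type |
| 3.2.1, Table 3 | One combined ANC-PNC proportion |
| 3.6, paragraph before Table 5 | Outcomes specific to a visit type called secondary |
| 3.8 | One variable, ECall; one model; no visit-type term |

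The first two rows fit two analyses. The last three, read literally, fit one.

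**2. What the literal model estimates**

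Let *w* be the share of ANC visits in the data. With a similar mix before and after training, a single training coefficient is approximately

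pooled effect = *w* × (ANC effect) + (1 − *w*) × (PNC effect).

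The exact weights depend on the variance components, so this is an approximation. Section 3.7 plans four ANC clients per HCP observed for ANC and the same number for PNC, so *w* is about 0.5. The effects below are assumptions:

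- ANC 0.20, PNC 0: 0.5 × 0.20 + 0.5 × 0 = **0.10**
- ANC 0.10, PNC 0.10: 0.5 × 0.10 + 0.5 × 0.10 = **0.10**
- ANC 0, PNC 0.20: 0.5 × 0 + 0.5 × 0.20 = **0.10**

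Three different findings about the primary outcomes give the same reported number. The number also moves with the mix: at an assumed *w* of 0.7, the first case gives 0.7 × 0.20 = 0.14.

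**3. Number of visits**

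Section 3.5.3 gives 576 to 864 women. This is reproduced as HCFs × HCPs × visits × periods:

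- 18 × 2 × 4 × 4 = 576
- 18 × 3 × 4 × 4 = 864

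That is one set of four visits per HCP and period. The ceiling of 12 observations per facility and step in sections 3.5.2 and 3.10 agrees (3 × 4 = 12). Box 2 and section 3.7 ask for four visits per HCP and period for each outcome:

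- 2 × 576 = 1,152
- 2 × 864 = 1,728

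So the same split between one outcome and two runs through the sampling plan.

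**4. The detectable difference**

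Section 3.6 uses the mean of four visits per HCP: SD = √(0.2²/4 + 3 × 0.15²) = √0.0775 = 0.278, and 0.81 × 0.278 = 0.23, as stated. This applies to each outcome if each has four visits per HCP and period. If four visits were instead shared equally, two of each type, then SD = √(0.2²/2 + 0.0675) = √0.0875 = 0.296. Holding the multiplier at 0.81, as Table 5 does, gives 0.81 × 0.296 = 0.24. On these assumptions the issue is mainly what is estimated, and much less power.

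**The case against.** The best reply is that section 3.8 never says the visit types are pooled. The slash in its description of visits can mean either one or the other, and section 3.7 uses the same form when describing an observation day. Section 3.6 says each interaction counts towards its corresponding outcome. ECall may therefore be a generic label, with the same model fitted once to each score; in that case no visit-type term is needed. This reading is tenable. A reader might infer that pooling is settled and that neither primary outcome will be estimated, and the protocol does not support so firm a statement. But section 3.8 does not state the charitable reading either, and Table 3, the remark on secondary outcomes and the totals for a single set of visits point the other way.

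Several further inferences should be resisted:

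- **Scale.** The two scores differ in content but not in scale. Both are proportions with components of equal weight, and most ANC components are carried into the PNC score.
- **Visit mix.** The ANC and PNC attendance counts in section 2.1.3 come from one month in 60 facilities across twelve regions. They are not the trial's sampling mix and should not be used to size the problem.
- **Change in mix.** The protocol gives no figure for a shift in visit mix after training. Where different staff run the two clinics, the HCP random effect would also absorb part of any difference in level. It would not, however, separate two training effects.
- **Multiplicity.** How two primary results lead to a conclusion is commonly left to the SAP, which is not shown. Its absence here is not a finding, and nothing in the protocol ranks ANC above PNC.

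**Conclusion.** The inconsistency stands. The protocol names two primary outcomes and then specifies one model for a differently named variable without saying how it relates to them. Taken literally, the analysis gives an effect weighted by visit mix that is neither primary outcome: about 0.10 where ANC improves by 0.20 and PNC not at all. That figure assumes those effects and the roughly equal mix of section 3.7. Whether pooling is intended cannot be determined from the protocol, so the claim is that the primary analysis is ambiguous and wrong as written, not that the trial is certain to miss both outcomes. An SAP that split the analysis would be correcting section 3.8, not merely filling in detail. The mismatch between 576 to 864 women and the implied 1,152 to 1,728 visits follows from the protocol's own counts and needs no assumption beyond them.

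**What to change.** - **Section 3.8:** replace ECall by two fits of the stated model, one to EC_ANC using ANC visits and one to EC_PNC using PNC visits. Report a training effect with its interval for each. Keep any pooled score as secondary or descriptive.
- **Table 3:** list both primary outcomes.
- **Section 3.6, paragraph before Table 5:** stop calling outcomes specific to a visit type secondary, or say which other outcomes are meant.
- **Sections 3.5.2, 3.5.3 and 3.10:** reconcile the limit of 12 observations per facility and step, and the total of 576 to 864, with Box 2 and section 3.7.

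The analysis change costs a few sentences and one extra model fit, with no new data. It should be made before outcomes are examined by training status, so that the choice between pooled and separate results is not driven by the data. Reconciling the totals is also wording if one set of visits is intended. If Box 2 and section 3.7 are to be followed, the stated number of women asked for consent doubles. An HCP observed for both visit types would then need at least two observation days per period, because section 3.10 allows no more than four observed consultations per HCP per day.
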